1.0 PROTOCOL SUMMARY AND/OR SCHEMA

Metastatic disease of the spine affects nearly 20% of patients with cancer and poses a growing problem as improved neo-adjuvant strategies allow longer life expectancy.

This is a Phase III multicenter clinical trial designed to prospectively evaluate the comparative effectiveness of single-fraction and hypofractionated stereotactic radiosurgery (SRS) in patients who underwent decompressive surgery for spinal metastases with a primary endpoint of local tumor control. Secondary objectives will evaluate complications and quality of life measures. Collaborating institutions include Massachusetts General Hospital (MGH), Johns Hopkins University (JHU), and Stanford University.

Eligible patients will have undergone spinal decompressive surgery for the treatment of high grade metastatic epidural spinal cord compression and demonstrate post-operative separation between tumor and the spinal cord on CT myelogram or MRI perfusion. This is a non-inferiority study in which patients will be randomized in a 1:1 ratio to undergo either single-fraction SRS (24 Gy) or high-dose hypofractionated SRS (27 Gy in 3 fractions) within 8 weeks of surgery. The treatment duration will be 1 to 7 days.

Study enrollment of 150 patients will be completed within two years. After randomization, patients will be followed up at 3, 6, 9, 12, 18, and 24 months (± 8 weeks) when possible or until death. The study duration will be up to four years. The primary endpoint will be local tumor control after SRS as monitored through imaging at follow up.

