3.0 BACKGROUND AND RATIONALE

3.1 Metastatic spine tumors

The incidence of metastatic spine tumors is nearly 20% and has been increasing due to improvements in neo-adjuvant strategies. These allow for longer patient survival and thus increased incidence of progression to metastatic disease¹. The median survival for patients undergoing surgery for spinal metastatic tumors ranges from 7.0 – 16.5 months²⁻⁶. More specifically, the median survival varies depending on the histological type of primary cancer^{2,4}. However, with the development of superior systemic therapies which extend survival, these numbers are becoming outdated.

Diagnosis of spinal metastasis is made reliably based on clinical, radiographic and histologic grounds. Metastases to the skeletal system are the third most often involved system after the lungs and liver. Of this, nearly half are metastases of the spine. The majority of spinal metastases involve disease of the vertebral body with or without epidural compression. It is estimated that 5-10% of patients with spinal metastases will develop symptomatic spinal cord compression requiring surgical intervention⁷. The NOMS paradigm provides a widely-accepted guide to relevant considerations (Neurologic, Oncologic, Mechanical and Systemic) when determining the optimal combination of systemic, radiation and surgical therapies for individual patients with spinal metastases⁸. Yet despite advances in surgical and radiologic treatments, local recurrence of spinal metastasis remains a challenging problem and can lead to progression of spinal column instability, nerve/spinal cord compression and may require repeat surgery^{9,10}. Further study on improving the local recurrence of spinal metastases is warranted and has great clinical implications for the evaluation and counseling of patients.

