3.3 Post-operative SRS

Spinal metastases exhibit a range of sensitivity to radiation therapy. In patients with previous radiation to the surgical site, and/or with primary tumor histologies that respond poorly to conventionally fractionated radiation, spinal SRS provides safe and durable local control. The efficacy and safety of post-operative SRS in the treatment of spinal metastatic tumors was recently described¹². Single-fraction SRS and high-dose hypofractionated SRS both provide excellent tumor control (9% vs 4.1% estimated 1-year cumulative recurrence incidence) after spinal decompression surgery for high grade spinal cord compression. These data suggest that high-dose hypofractionated SRS may provide superior local tumor control compared to single-fraction SRS, however our retrospective study was not powered to detect this difference. The current trial is designed to evaluate whether single-fraction SRS provides comparable local control to high-dose hypofractionated SRS.

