10.0 EVALUATION DURING TREATMENT/INTERVENTION

Pre-treatment evaluations may be performed within 8 weeks of consent. After SRS, patients will be closely monitored for any evidence of toxicity, systemic illness or tumor progression. Acute toxicity assessment (see Appendix E) will occur by phone or clinic visit within 4 weeks (± 10 days) after the completion of radiotherapy. Follow-up clinic visits will take place 3 months, 6 months, 9 months, 12 months, 18 months and 24 months (± 8 weeks) after the completion of radiotherapy. At each follow-up visit, the investigators will complete the Spine Clinic Assessment form (see Appendix F). Spine MRI or CT will also be performed at the time of each follow-up, in accordance with routine standard of care.

Table 1: Pre-therapy and Follow-up Evaluations

Item	Pre-therapy (w within 8 weeks of consent)	Follow-up (3, 6, 9, 12, 18, 24 months \pm 8 weeks after the completion of SRS)
Inclusion/exclusion criteria	X	
CT myelogram or MRI perfusion	X	
Pathology diagnosis confirming metastatic disease	X	
Medical history	X	
Pregnancy test ¹	X	
Physical exam	X	X
Concomitant medications review	X	X
ECOG	X	X
Quality of Life assessments (MDASI and BPI) ²	X	X
Spine Clinic Assessment Form	X	X
MRI/CT scan ³	X	X
Adverse-event/toxicity assessment ⁴	X	X
Consent	X	

¹ For women of child-bearing potential, a urine or blood pregnancy test must be completed within 2 weeks prior to SRS.

- ² Patients will be asked to complete quality of life (MDASI and BPI) assessments at all timepoints, however this will remain optional. In instances where these questionnaires are not available in the participant's primary language, the participant will not be required to complete the questionnaire(s).
- ³ All patients are required to have MRI/CT based imaging at baseline and 3, 6, 9, 12, 18, and 24 months (\pm 8 weeks) after SRS. The imaging modality should remain constant for each patient throughout.
- ⁴ Only treatment-related adverse events will be reported. Acute toxicity assessment (see Appendix E) will occur by phone or clinic visit within 4 weeks (\pm 10 days) after the completion of radiotherapy.

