An intent-to-treat, stratified log rank test will be used to test whether or not the single-fraction SRS arm is inferior to the hypofractionated (3 fractions in total) SRS arm in terms of the local control rate. To set up a formal test we will use the 1-year local control rate as the surrogate of the efficacy (assuming that the two survival curves follow exponential distributions) and allow a 10% inferior margin. From a clinical standpoint, the investigators agreed that a difference of less than 10% is not regarded as significant. On this basis, we permit a 10% inferior margin. I.e., we will test $H_0: P_1 \leq (P_2 - 10\%)$ vs $H_1: P_1 > (P_2 - 10\%)$, where P_1 and P_2 denote the 1-year local control rate for the single-fraction arm and the 3-fraction arm, respectively. To approximately assess the power of the test, we estimate that the 3-fraction arm will yield a 1-year local control rate around 85% based on interim preliminary data from a multicenter Phase III trial (Protocol 10-154), and set the type I error (that is, declare single-fraction arm noninferior while it is not) rate at 0.10. When the two arms have equal efficacy, i.e., $P_1 = P_2 = 85\%$, the power (that is, declare the single-fraction arm noninferior while it is) of this noninferiority test⁴⁰ is 80% when there are 75 patients in each arm. Besides, since deaths without local failure are likely, competing risk analysis will also be used to estimate the local control rates of the two arms over time. We plan to enroll 150 patients within 2 years. If a

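### The stated 80% power holds only if no patient dies and all are followed to study end; with the survival the protocol quotes it is about 46–70%

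*Combined protocol and SAP*

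**What the plan says.** Section 14.0 plans a stratified, intent-to-treat log-rank test for noninferiority of single-fraction SRS. Its inputs are exponential curves, 85% one-year local control in both arms, a 10-point margin and type I error 0.10. From these it concludes that the power "is 80% when there are 75 patients in each arm". It presents this as an approximate assessment. No required number of failures, death rate or dropout rate is given.

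The next sentence of Section 14.0 reads "since deaths without local failure are likely, competing risk analysis will also be used". It uses this only to add an estimate of control rates over time and does not return to power.

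On survival, Section 3.1 says "The median survival for patients undergoing surgery for spinal metastatic tumors ranges from 7.0 – 16.5 months", then adds that "with the development of superior systemic therapies which extend survival, these numbers are becoming outdated". Section 3.3 gives the earlier retrospective results as cumulative incidence: "9% vs 4.1% estimated 1-year cumulative recurrence incidence".

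On follow-up, Section 1.0 says "patients will be followed up at 3, 6, 9, 12, 18, and 24 months (± 8 weeks) when possible or until death" and "The study duration will be up to four years". Section 10.0 has the same last visit: "Follow-up clinic visits will take place 3 months, 6 months, 9 months, 12 months, 18 months and 24 months". Section 14.0 plans two-year accrual and two further years after the last patient enters.

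**The concern.** The power of a log-rank test depends on the number of events observed, here local failures. A patient who dies without local failure contributes none. In a population with median survival near or below a year and a half, deaths remove a large share of the failures that would otherwise be seen over 2 to 4 years. A power figure that leaves deaths out is then too high.

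This is the only power justification for the primary endpoint of a Phase III noninferiority trial. If it is overstated, two equally effective schedules have a much larger chance of an inconclusive result than the plan admits. The DSMB and readers would also judge such a result against a power the trial never had.

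**Working it through.** **Inputs from the protocol.** 150 patients, 1:1; control 85% and margin 10 points at one year; exponential failure times; one-sided 0.10; accrual 2 years plus 2 years (Section 14.0); last scheduled visit at 24 months (Sections 1.0 and 10.0); median survival 7.0–16.5 months (Section 3.1).

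**Assumptions added here.** Uniform accrual; exponential deaths, independent of local failure and equal in the two arms; no loss to follow-up.

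**Step 1: failures needed.** Hazard at 85%: −ln 0.85 = 0.1625 per year. Hazard at 75%: −ln 0.75 = 0.2877 per year. Margin hazard ratio = 0.2877/0.1625 = 1.770, with log 0.571.

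D = 4 × (1.2816 + 0.8416)² / 0.571² = 55.3 local failures for 80% power.

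**Step 2: the plan's own figure.** Power = Φ(√(D/4) × ln HR − 1.2816). With no deaths, P(failure by T) = 1 − exp(−0.1625 T).

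- T uniform on 2 to 4 years (study end): P = 0.383, D = 150 × 0.383 = 57.5, power 81%. This reproduces the stated 80%.
- T = 2 years for everyone: P = 0.2775, D = 41.6, power 71%.

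Other variants without deaths also miss 80%: two-sided 0.10 gives 70%, four years for every patient 87%, and a binary comparison at one year 67%.

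**Step 3: add deaths.** With death hazard μ = ln 2 / median survival, P(failure by T) = λ/(λ+μ) × (1 − exp(−(λ+μ)T)), averaged over T where T varies. The hazards are μ = 1.188 per year (7.0 months) and 0.504 per year (16.5 months).

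The plan does not say what 85% measures, so both readings were run:

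- *Death-censored control:* λ = 0.1625, HR 1.770, 55 failures needed.
- *1 minus cumulative incidence:* λ is solved so that one-year incidence is 15% and 25%. At 7.0 months this gives 0.287 and 0.522 per year (HR 1.82, 50 failures needed). At 16.5 months it gives 0.210 and 0.376 per year (HR 1.79, 53 needed).

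| Median survival | Follow-up | Death-censored: failures / power | Cumulative incidence: failures / power |
|---|---|---|---|
| 7.0 months | stops at 24 months | 16.8 / 45.6% | 27.6 / 61.5% |
| 7.0 months | to study end | 17.6 / 46.7% | 28.7 / 62.6% |
| 16.5 months | stops at 24 months | 26.9 / 57.9% | 33.5 / 65.8% |
| 16.5 months | to study end | 31.2 / 62.3% | 38.5 / 70.1% |

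So 17–31 failures are expected where 55 are needed, or 28–39 where 50–53 are needed.

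**Step 4: simulation.** A simulated noninferiority score test (6,000 trials per scenario, death-censored reading) gave, to study end / with the 24-month stop: no deaths 81% / 71%; 7.0 months 47% / 45%; 16.5 months 62% / 58%.

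**Step 5: longer survival (assumed medians, because Section 3.1 calls its figures outdated).**

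| Median survival | Death-censored: 24-month stop / study end | Cumulative incidence: 24-month stop / study end |
|---|---|---|
| 24 months | 62% / 68% | 67% / 73% |
| 36 months | 65% / 72% | 69% / 75% |
| 60 months | 67% / 75% | 69% / 78% |

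No case reaches 80%.

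**Step 6: interim looks.** All figures above are for a fixed design. The four-look boundary costs about 1–3 further points if looks fall at years 1 to 4, which is an assumption; the plan ties them only to annual DSMB review.

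**The case against.** The strongest reply is that nothing was miscalculated. The 80% reproduces from Section 14.0's own inputs, the text calls the assessment approximate, and the omission of deaths is inferred rather than stated. That is fair as a description: the fault is an unstated assumption, not a slip in the formula. But the plan itself expects deaths without local failure, so the figure does not describe this design.

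The survival range may also be pessimistic. Section 3.1 discounts it, and patients must have a life expectancy of at least 3 months and be randomized after surgery. The 7-month end, which produces the 46%, is probably the least applicable. At 16.5 months the range is 58–70%. With medians of 24–36 months, study-end follow-up and the cumulative-incidence reading, the gap shrinks to 5–7 points, which the word approximate might cover. It does not cover the 10 to 34 points under the survival the protocol quotes.

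Deaths are not the only cause. If follow-up stops at 24 months, power is already 71% with no deaths. The follow-up passages can be read together, since a four-year study fits two years of accrual plus the last patient's 24 months. What stays open is whether earlier patients are imaged beyond 24 months, and the 80% depends on that.

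The analysis is by lesion, so units may exceed 150. The plan expects very few patients with several lesions; 5–10% more independent units would add about 1–3 points.

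**Conclusion.** The concern holds. The stated 80% matches a design with no deaths and follow-up to study end. With the protocol's quoted survival, power is about 46–62% on the death-censored reading, which is closer to the log-rank test and exponential curves in the plan, and about 62–70% on the cumulative-incidence reading. The 70% needs the longest quoted median, follow-up to study end and the cumulative-incidence reading all at once.

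Two truly equal arms would fail to be declared noninferior in about 30–54% of such trials instead of 20%. Type I error is not affected. The exact figures rest on exponential, independent deaths that are equal between arms, uniform accrual and no loss to follow-up. The conclusion that power is below 80% holds for every median survival examined, up to an assumed 60 months.

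**What to change.** Restate the power sentence in Section 14.0 so that it gives:

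- the number of local failures required (about 55 on the death-censored reading, 50–53 on the cumulative-incidence reading at the quoted survival);
- the survival and loss-to-follow-up assumptions;
- whether 85% is death-censored control or 1 minus cumulative incidence;
- the expected failures and the power as a range under those assumptions.

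Add one sentence stating whether patients enrolled early are imaged beyond 24 months, so that Sections 1.0, 10.0 and 14.0 agree. Compute any power figure that uses the four-look boundary at the actual planned look times.

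The cost is amended wording in Section 14.0, one follow-up sentence and a less favourable stated power. The test, margin and sample size can stay as they are; no added patients are needed to make the statement correct.

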patient has multiple eligible lesions, all of them will be treated within the randomized arm and each eligible lesion (non-contiguous lesions treated with a separate radiation contour) will be treated as a separate study unit. After the enrollment of the final patient, a 2-year follow up is planned. Three interim analyses are planned and will be conducted at the time of the DSMB annual review of the study. The O'Brien-Flemming boundary will be applied for assessing statistical significance. Specifically, the rejection regions in terms of the corresponding Z-scores are $Z > 3.09$, $Z > 2.06$, $Z > 1.63$ and $Z > 1.39$ for the three interim looks and the final look, respectively. We expect that very few patients will have multiple lesions and thus we do not plan to examine the correlation among multiple lesions from the same patients. Instead, the analysis of the primary endpoint will be conducted at lesion level as mentioned above. Data will be collected from all four centers and analyzed at MSKCC.

In consideration of the fact that a large cohort will be recruited, this study will be continuously monitored to protect patients from excess toxicity. For each arm, we anticipate that the true rate of any grade 4 toxicity within 24 months post SRS is less than 10%. All grade 4 toxicities or greater observed will be reviewed by the study chair. Moreover, using a stopping rule based on sequential probability ratio test (SPRT), each arm of the study is monitored for any grade 4 or above toxicities that are judged to be associated with the radiation treatment. This stopping rule specifies that for each arm, the study will be halted if any of the following conditions occur: >4 /first 15; >6 /first 35; >9 /first 55; or if more than 12 unacceptable toxicities are observed within 24 months post SRS when the last (75th) patient has completed the trial. When the true toxicity rate is 10%, this stopping rule has a probability of 0.1 to stop the trial. When the true toxicity rate is 20%, this stopping rule has a probability of 0.8 to stop the trial. For this stopping rule we will use each patient as a study unit.

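### The toxicity rule's stated 0.8 chance of stopping is an end-of-follow-up figure that counts a look made after all patients are treated; the chance of stopping during accrual is lower and is not given

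*Combined protocol and SAP*

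**What the plan says.** Section 14.0 (Biostatistics) introduces the rule by saying that "this study will be continuously monitored to protect patients from excess toxicity". Each arm is monitored for radiation-related toxicity of grade 4 or above, with the patient as the unit, and the anticipated 24-month rate is below 10%. For each arm, "the study will be halted if any of the following conditions occur: >4 /first 15; >6 /first 35; >9 /first 55". A fourth condition is met "if more than 12 unacceptable toxicities are observed within 24 months post SRS when the last (75th) patient has completed the trial".

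Two operating characteristics follow: "When the true toxicity rate is 10%, this stopping rule has a probability of 0.1 to stop the trial", and "When the true toxicity rate is 20%, this stopping rule has a probability of 0.8 to stop the trial".

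The timetable is in the same section: "We plan to enroll 150 patients within 2 years", with 75 per arm, and two further years of follow-up after the last enrollment. The section gives no assumption about when toxicities occur. It does not say how patients with incomplete follow-up count at 15, 35 and 55, and it gives no probability of stopping during accrual.

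**The concern.** A toxicity stopping rule protects patients by sparing those not yet treated. A board reading 0.8 will naturally take it as the chance that a 20% rate is caught in time to do so. Two features work against that reading. The fourth condition is assessed only after everyone in the arm has been treated and followed. And accrual is as long as the toxicity window, so essentially nobody has a complete 24-month outcome before enrollment closes. What is at stake is how much protection the board believes the rule gives; the boundaries themselves are not in question.

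**Working it through.** **Inputs (section 14.0).** Limits per arm: more than 4 of 15, 6 of 35, 9 of 55, 12 of 75. True rates 10% and 20%. 75 per arm over 24 months, then 24 months of follow-up.

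**Step 1: reproduce the printed figures.** Assume every patient's 24-month outcome is known. Let f_k(x) be the probability of x events among the first n_k patients with no earlier crossing:

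f_k(x) = Σ over y ≤ c_(k−1) of f_(k−1)(y) × Bin(x − y; n_k − n_(k−1), p)

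The probability of first crossing at look k is the sum of f_k(x) over x > c_k.

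| Look | First crossing, p = 0.20 | Cumulative | First crossing, p = 0.10 | Cumulative |
|---|---|---|---|---|
| 15 | 0.164 | 0.164 | 0.013 | 0.013 |
| 35 | 0.411 | 0.575 | 0.047 | 0.060 |
| 55 | 0.158 | 0.733 | 0.019 | 0.078 |
| 75 | 0.089 | 0.822 | 0.010 | 0.088 |

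The totals, 0.822 and 0.088, round to the printed 0.8 and 0.1. Other readings fit worse: limits read as at-least give 0.904 and 0.191; the last look alone gives 0.760 and 0.034; either of two arms crossing gives 0.968 and 0.168.

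**Step 2: remove the fourth condition.** 0.822 − 0.089 = 0.733 at 20%, and 0.088 − 0.010 = 0.078 at 10%. The printed 0.8 therefore needs the fourth condition, since 0.733 rounds to 0.7. The 10% figure rounds to 0.1 either way.

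**Step 3: calendar.** With even entry, patient i in an arm enters at month 24 × i / 75 = 0.32 × i. Patients 15, 35, 55 and 75 enter at months 4.8, 11.2, 17.6 and 24.0 and finish their windows at 28.8, 35.2, 41.6 and 48.0. The fourth condition therefore falls at about month 48.

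**Step 4: chance of crossing before accrual closes.** Count events as they occur. The limit of c among the first n is crossed at the (c + 1)th earliest event date among those n patients. Simulation: 100,000 trials per pattern, true rate 20%, treatment at entry, no deaths. The onset patterns are assumptions.

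| Assumed onset after SRS | Before month 24, limits at 15, 35, 55 | Before month 24, 75-patient count also run in real time | Share of 0.82 arising after month 24 (second column) |
|---|---|---|---|
| All after month 6, uniform to 24 | 0.22 | 0.22 | 74% |
| Uniform over 24 months | 0.31 | 0.31 | 62% |
| 2/7 in first 3 months, rest uniform to 24 | 0.38 | 0.38 | 54% |
| Half in first 3 months, rest uniform to 24 | 0.48 | 0.49 | 41% |
| All within 12 months | 0.67 | 0.67 | 19% |
| All within 6 months | 0.73 | 0.75 | 9% |
| All within 3 months | 0.73 | 0.78 | 6% |

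The 2/7 row uses the only onset split in the document: two acute and five late grade 4–5 esophageal events in section 3.7. That is a small series for a single organ, so it is indicative only.

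**The case against.** A reader might infer that most of the 0.8 arises after everyone has been treated, or that the rule has no chance of stopping before accrual ends. The documents support neither.

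- **The last look is a minor contributor.** It supplies 0.089 of 0.822, or 11%. The first three limits supply 0.733.
- **Zero chance during accrual is a strained reading.** It requires each look to wait for complete 24-month outcomes. The completion wording attaches only to the fourth condition. The limits at 15, 35 and 55 carry no such requirement, and the stated aim is continuous monitoring. Reporting is also prompt: 14 days for adverse events (section 11.2), and 3 calendar days from sites for serious ones (section 17.3).
- **The post-accrual share depends on onset.** In the table it runs from 6% to 74%, and it is below half once half the events are early.
- **Deaths can move the answer.** Section 3.1 gives median survival of 7.0 to 16.5 months. If 20% is the observed rate and onset is weighted by exponential survival at those medians, crossing before month 24 rises to about 0.4 to 0.6 for the uniform and 2/7 patterns. If 20% is instead a rate before deaths intervene, overall stopping falls, to 0.24 and 0.02 under uniform onset at medians of 16.5 and 7.0 months. The documents do not say which is meant.
- **The printed figures are arithmetically right.** They are ordinary full-sample operating characteristics, and section 14.0 never says that 0.8 refers to the accrual period.

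All of this stands. It does not answer the narrower point. A figure described as the probability of stopping the trial includes a look that cannot stop it and takes no account of calendar time, in a rule offered as patient protection.

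**Conclusion.** The concern holds in this limited form. The 0.8 (exact 0.82) assumes complete 24-month outcomes and counts a condition that cannot halt anything. The four-limit figure falls to 0.73 at a 20% rate, and from 0.09 to 0.08 at 10%, once that condition is set aside. The chance of stopping while patients can still be spared treatment is below 0.8 and is not stated. With events counted as they occur, it is about 0.3 under uniform onset, about 0.75 if all onset is within 3 months (0.73 to 0.78, depending on whether the 75-patient count also runs in real time), and about 0.2 if all onset is after 6 months.

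The 0.73 and 0.08 are exact and need no timing assumption. The during-accrual range rests on even entry of 75 per arm over 24 months, treatment at entry, no deaths and assumed onset patterns. It shows how widely the answer can vary and is not an estimate for this trial.

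**What to change.** Keep all four boundaries as they are. In section 14.0:

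1. Label the 75-patient condition an end-of-trial assessment, not a stopping condition.
2. Restate the probability of stopping from the first three limits: 0.73 at a 20% rate and 0.08 at 10%.
3. Add the probability of crossing before accrual closes under two or three stated onset assumptions, and say whether the 20% rate is taken with deaths included.
4. Confirm that the limits at 15, 35 and 55 apply to events as they occur, in line with the stated continuous monitoring.

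The cost is a few sentences and a short simulation; no threshold, sample size or data collection changes. The downside is that the published stopping probability becomes less favorable.

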14.0 BIOSTATISTICS

The primary endpoint of this multicenter Phase III noninferiority study is the local tumor control after post-operative spinal stereotactic radiosurgery (SRS). A noninferiority study design is justified on the basis that both treatment options have their advantages and disadvantages with currently mixed data about the relative tumor control offered by hypofractionated and single-fraction SRS. Some data suggest that single-fraction SRS may offer superior local control and since only one treatment visit is required it is cheaper and more convenient for patients. On the other hand, data suggest that single-fraction treatment may be associated with a higher risk of vertebral body fractures, which is considered a treatment-related toxicity. Determining whether single-fraction SRS and hypofractionated SRS offer comparable local tumor control will allow physicians to make treatment decisions based on factors such as cost and toxicity risk.

Lack of local radiographic progression will be defined as local tumor control. Patients will be randomized in a 1:1 fashion and the local control in the two treatment arms (single-fraction SRS vs. hypofractionated SRS) will be assessed. The patients will be stratified according to participating center (MSK, MGH, JHH, Stanford), presence or absence of prior radiation history at the study level, and radioresistance of the primary tumor histology, with breast and prostate classified as radiosensitive and the remaining solid tumor metastases (i.e. melanoma, sarcoma, thyroid, renal, colorectal) classified as radioresistant.

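### The 0.1 and 0.8 stopping probabilities for the toxicity rule are single-arm values described as trial-level; if either arm halts the study, the figure at a 10% rate in both arms is about 0.17

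*Combined protocol and SAP*

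**What the plan says.** All of the relevant text is in section 14.0 (Biostatistics), in the paragraph on toxicity monitoring.

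- The unit monitored is the arm: "each arm of the study is monitored for any grade 4 or above toxicities that are judged to be associated with the radiation treatment".
- The consequence of a crossing is worded for the study: "This stopping rule specifies that for each arm, the study will be halted if any of the following conditions occur".
- The limits are ">4 /first 15; >6 /first 35; >9 /first 55", followed by "or if more than 12 unacceptable toxicities are observed within 24 months post SRS when the last (75th) patient has completed the trial".
- Two operating characteristics follow: "When the true toxicity rate is 10%, this stopping rule has a probability of 0.1 to stop the trial", and "When the true toxicity rate is 20%, this stopping rule has a probability of 0.8 to stop the trial".

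The same paragraph expects a true grade 4 rate below 10% in each arm and counts patients, not lesions, for this rule. No sentence says whether 0.1 and 0.8 refer to one arm or to the two-arm trial, and no separate two-arm probability is given.

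**The concern.** Two arms run the same rule side by side, and the text says that the study halts when the rule is met in an arm. The study then has two chances to be halted, so the probability of halting it must exceed the probability that one given arm crosses (unless the other arm cannot cross). A figure worked out for one arm cannot also be the figure for the trial.

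These two sentences are the only operating characteristics given for the toxicity rule. A monitoring board or IRB that takes them at face value would put the risk of a false stop at the 10% reference rate at 0.1. There is also a practical question: if one arm crosses, the reader needs to know whether the whole randomised study or only that arm halts, and the wording does not settle this cleanly.

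**Working it through.** **Inputs (section 14.0).** Limits per arm: stop if the cumulative count exceeds 4 of 15, 6 of 35, 9 of 55 or 12 of 75. Arm size: the power statement "is 80% when there are 75 patients in each arm", with 1:1 allocation. Reference rates: 10% and 20%. Unit: the patient, so a binomial count applies.

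**Step 1: reproduce the plan's figures for one arm.** Let X(n) be the number of patients with a qualifying toxicity among the first n in the arm. The stopping probability is

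P(stop, one arm) = P[X(15) > 4, or X(35) > 6, or X(55) > 9, or X(75) > 12].

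It is computed exactly by carrying the binomial distribution of X(n) from look to look and removing the paths that have already crossed.

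| True rate | First crossed at 15 | at 35 | at 55 | at 75 | One-arm total | Plan states |
|---|---|---|---|---|---|---|
| 10% | 0.0127 | 0.0468 | 0.0185 | 0.0097 | 0.0877 | 0.1 |
| 20% | 0.1642 | 0.4106 | 0.1584 | 0.0886 | 0.8218 | 0.8 |

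Both totals round to the printed figures. Checking after every patient instead of only at the four looks gives the same totals. A simulation of 200,000 arms gave 0.088 and 0.820. Other readings of the limits fit worse:

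- reaching the limit instead of exceeding it: 0.191 and 0.904
- every limit raised by one: 0.037 and 0.715
- final look only: 0.034 and 0.760

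**Step 2: either arm halts the study.** For independent arms A and B,

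P(study halted) = 1 − (1 − p_A)(1 − p_B),

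where p_A and p_B are the one-arm probabilities. Which arm crosses first does not matter, because the first crossing already halts the study.

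- Both arms at 10%: 1 − (1 − 0.0877)² = 0.168
- Both arms at 20%: 1 − (1 − 0.8218)² = 0.968
- One arm at 10%, the other at 20%: 1 − (0.9123 × 0.1782) = 0.837

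Starting from the plan's rounded values instead gives 1 − 0.9² = 0.19 and 1 − 0.2² = 0.96. On neither route do the equal-rate values round to 0.1 and 0.8, so the printed pair describes one arm.

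**Step 3: rates below 10%.** The plan expects the rate to be under 10%, so the same formula is applied there.

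| True rate in both arms | One arm | Either arm |
|---|---|---|
| 10% | 0.088 | 0.168 |
| 9% | 0.052 | 0.102 |
| 8% | 0.028 | 0.056 |
| 5% | 0.002 | 0.004 |

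**The case against.** The strongest reply is that the paragraph is framed by arm throughout. The anticipated rate, the monitoring and the limits are all given per arm, and the two probability sentences speak of one rule and one true rate. A statistical reader may well take 0.1 and 0.8 as per-arm values and regard the mention of the trial as loose wording. That reading is plausible, and on it the numbers are right. It does not remove the problem, because the statements that the study is halted and that the trial is stopped would then be the wrong part. One or the other has to change.

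Three stronger conclusions are tempting, and the documents do not support them.

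- *The plan's calculation is wrong.* It is not. The one-arm figures reproduce at the precision printed, so the fault lies in the unit they are attached to.
- *The false-stop risk is about 0.17 whenever toxicity is acceptable.* That value belongs to both arms at exactly 10%, the edge of the range the plan expects. At 9% in both arms the either-arm figure is about the stated 0.1, and below that the stated 0.1 overstates the risk. Section 11.1 describes the more significant toxicities as occurring in under 1% of patients.
- *Patients are less well protected than stated.* The reverse holds under the literal reading. The chance of halting is 0.84 with one arm at 20% and 0.97 with both, each above the stated 0.8.

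It is also fair to say that 0.168 is idealised. It needs all 75 patients per arm to be evaluable for toxicity to 24 months, while section 3.1 cites median survival of 7.0 to 16.5 months after surgery for spinal metastases. The same idealisation underlies the plan's own 0.1 and 0.8, so it does not favour either figure.

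**Conclusion.** The point holds as a mislabelled operating characteristic together with an unresolved inconsistency of unit. The printed 0.1 and 0.8 are single-arm probabilities (exact 0.088 and 0.822) presented as probabilities for the trial. Under the literal reading, the trial-level false-stop probability with both arms at 10% is about 0.17. That is roughly 7 percentage points above the stated 0.1; put the other way, the stated figure is about 40% too low (0.1 / 0.168 = 0.60).

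The size rests on independent arms and patients, 75 evaluable patients per arm, a true rate of exactly 10% in both arms, and a crossing in either arm halting the whole study. If only the affected arm is meant to halt, 0.1 and 0.8 stand as per-arm figures and the wording about the study and the trial is what needs correcting. Which of these the sponsor intends cannot be determined from the documents.

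**What to change.** Three edits to the toxicity paragraph in section 14.0:

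1. Label 0.1 and 0.8 (more exactly 0.09 and 0.82) as the probability that the rule is met in one arm.
2. Add the trial-level values and their assumptions: the probability that at least one arm meets the rule is 0.17 with both arms at 10%, 0.97 with both at 20%, and 0.84 with one arm at each rate, for independent arms and 75 evaluable patients per arm. A line giving 0.10 at 9%, 0.056 at 8% and 0.004 at 5% would show how quickly the false-stop risk falls over the range the plan expects.
3. Reconcile the per-arm wording with the statements that the study is halted and the trial stopped, so that the text says which unit a crossing halts and which unit each probability refers to. That choice is the sponsor's.

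The cost is a sentence or two. No limit, sample size or analysis changes. The only downside is that the stated false-stop figure becomes less favourable.
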